5.3.2.6 Partial Remission (PR)

For subjects to be classified as being in PR, they must have bone marrow regenerating normal hematopoietic cells with evidence of peripheral recovery with no (or only a few regenerating) circulating blasts and with a decrease of at least 50% in the percentage of blasts in the bone marrow aspirate/biopsy with the total marrow blasts between 5% and 25%.

5.3.2.7 Relapse

Relapse after CR, CRp or CRi is defined as a reappearance of leukemic blasts in the peripheral blood or $\geq 5\%$ blasts in the bone marrow aspirate/biopsy not attributable to any other cause or reappearance or new appearance of extramedullary leukemia.

Relapse after PR is similarly defined with reappearance of significant numbers of peripheral blasts and an increase in the percentage of blasts in the bone marrow aspirate/biopsy to $> 25\%$ not attributable to any other cause or reappearance or new appearance of extramedullary leukemia.

5.3.2.8 Treatment Failure

Treatment failure is defined as lack of CR, CRp or CRi, and is determined at the EOT.

5.3.2.9 Best Response

Best response is defined as the best-measured response (CR, CRp, CRi or PR) post treatment. Two best responses will be defined.

5.3.3 Survival Time, Duration of Response and Other Efficacy Endpoints

5.3.3.1 Survival Status and Subsequent Antileukemic Treatments and Their Outcomes

Information on survival status, subsequent antileukemic treatments (including HSCT) and outcomes will be collected for all subjects during long-term follow-up.

The first survival status assessment will occur at the 30-day follow up. After the 30-day follow up, the subject or caregiver will continue to be contacted via telephone by site personnel for follow-up every 3 months. Data may be supplemented by site records when available at the time of the contact (e.g., treatment records, outcomes). Follow-up will continue until the data cut-off date for final analysis, which is estimated to be up to 3 years of follow-up for some subjects. Additional contacts may be made to support key analyses (e.g., final analysis).

Reasonable effort should be made to contact any subjects lost to follow-up during the course of the study in order to complete study-related assessments and retrieve any outstanding data and study drug. Following unsuccessful telephone contact, an effort to contact the subject by mail using a method that provides proof of receipt should be attempted. Contact via an alternate, preapproved contact is permissible if the subject is not reachable. Such efforts should be documented in the source documents.

If a subject death occurs during the SAE reporting period or if the death occurs after the SAE reporting period but is determined by the investigator to be related to study regimen (gilteritinib and/or atezolizumab), then the associated AE with outcome of death will also be reported on the AE eCRF and SAE Worksheet. If a subject death does not meet the criteria of an SAE, then death and antileukemic treatment and outcome up through the date of death should be collected and entered in the eCRF.

5.3.3.2 Overall Survival

OS is defined as the time from the date of enrollment until the date of death from any cause. For a subject who is not known to have died by the end-of-study follow-up, OS is censored at the date of last contact.

Date of last contact is defined as the death date or the latest of the following dates: treatment discontinuation date, last dosing administration date, last disease assessment date or the last follow-up date on which the subject was known to be alive.

5.3.3.3 Event-free Survival

EFS is defined as the time from the date of enrollment until the date of documented relapse from CR, CRp or CRi, treatment failure or death from any cause, whichever occurs first.

If a subject experiences relapse or death the subject is defined as having an EFS event related to either “relapse” or “death,” and the event date is the date of relapse or death.

If a subject who discontinues the treatment due to treatment failure during the first 2 treatment cycles, and the subject has no previous response of CR, CRp or CRi, the subject is defined as having an EFS event and the event date is the date of enrollment.

If a subject who discontinues the treatment due to treatment failure after the 2 treatment cycles, and the subject has no previous response of CR, CRp or CRi, the subject is defined as having an EFS event and the event date is the date of end of the 2nd treatment cycle evaluation date (i.e., cycle 3/day 1 bone marrow evaluation).

For a subject who is not known to have relapse or treatment failure or death, EFS is censored at the date of last relapse-free assessment date. Subject is not censored at HSCT.

5.3.3.4 Duration of Remission

Duration of remission includes duration of CRc, CR, CRi, CRp and response (CRc + PR).

Duration of CRc is defined as the time from the date of first CRc until the date of documented relapse for subjects who achieve CRc. Subjects who die without report of relapse are considered nonevents and censored at their last relapse-free disease assessment date. Subjects who come off study for an allogeneic HSCT will be considered nonevents and censored at the time of HSCT. Other subjects who do not relapse on study are considered nonevents and censored at the last relapse-free disease assessment date.

The duration of CR, CRp or CRi is defined similarly as duration of CRc.

Duration of response is defined as the time from the date of either first CRc or PR until the date of documented relapse of any type for subjects who achieve CRc or PR. Subjects who die without report of relapse are considered nonevents and censored at their last relapse-free disease assessment date. Subjects who come off study for an allogeneic HSCT will be considered nonevents and censored at the time of HSCT. Other subjects who do not relapse on study are considered nonevents and censored at the last relapse-free assessment date.

5.4 Safety Assessment

5.4.1 Vital Signs

Vital signs, including systolic and diastolic blood pressures (mmHg), radial pulse rate (beats/minute) and temperature will be obtained and recorded at the times specified in the Schedule of Assessments [Table 1]. All vital sign measurements will be obtained with the subject in the sitting or supine position.

If clinically significant vital sign changes from baseline (pretreatment) are noted, the changes will be documented as AEs on the AE page of the eCRF. Clinical significance will be defined as a variation in vital signs, which has medical relevance that could result in an alteration in medical care. The investigator will continue to monitor the subject until the parameter returns to grade ≤ 1 or to the baseline (pretreatment) value or until the investigator determines that follow up is no longer medically necessary

5.4.2 Laboratory Assessments

Refer to [Appendix 12.8 Laboratory Assessment] and laboratory manual for a list of the laboratory tests that will be performed during the conduct of the study. Refer to the Schedule of Assessments [Table 1] for study visit collection dates. Local laboratory tests can be used at screening for eligibility for serum chemistry, hematology, urinalysis and coagulation only. In

the event that the central laboratory results received after enrollment are not within eligibility parameters, the subject will still be considered eligible if local labs met the eligibility criteria and not considered a protocol deviation. Additional laboratory tests should be performed according to institutional standard of care. Local testing of hematology and bone marrow aspirate and/or biopsy at screening and day 1 of each cycle will be reported in the eCRF. Hematology results will need to be assessed prior to dosing.

Clinical significance of out-of-range laboratory findings is to be determined and documented by the investigator/subinvestigator who is a qualified physician.

5.4.3 Physical Examination

Standard, full physical examinations will be performed to assess general appearance, skin, eyes, ears, nose, throat, neck, cardiovascular, chest and lungs, abdomen, musculoskeletal, neurologic status, mental status and lymphatic systems. Genitourinary and rectal system examinations are to be performed only if clinically indicated. Physical examinations will be conducted at the visits outlined in the Schedule of Assessments [Table 1]. Each physical examination will include the observation and review of body system, weight at screening and on day 1 of each cycle. Height is only required at screening. If clinically significant worsening of findings from predose (day 1) is noted at any study visit, the changes will be documented as AEs on the AE page of the eCRF. Clinical significance is defined as any variation in physical findings, which has medical relevance that could result in an alteration in medical care. The investigator will continue to monitor the subject until the parameter returns to grade ≤ 1 or to the baseline (pretreatment) condition or until the investigator determines that follow up is no longer medically necessary.

5.4.4 Electrocardiogram

A 12-lead ECG will be performed during the screening period, predose of cycle 1/day 1, cycle 1/day 8, cycle 1/day 15, day 1 of each subsequent cycle, day 15 of each subsequent cycle and at the EOT visit. Predose assessments should be taken within 1 hour before gilteritinib alone or in combination with atezolizumab administration on the days when the combination is given. The 12-lead ECGs will be recorded in triplicate (3 separate ECGs, 10 minutes resting prior to first ECG and at least 5 minutes apart per time point) and transmitted electronically for central reading. The mean QTcF of the triplicate ECG tracings based on central reading will be used for all treatment interruption and reduction decisions.

If the mean triplicate QTcF is > 500 ms at any time point, on local read, the ECG will be repeated (within 2 hours if identified on machine read or as soon as possible if identified from central read). Cardiology consult will be obtained as medically indicated. If QTcF > 500 ms is confirmed, then the investigator will interrupt and reduce gilteritinib per the interruption or reduction guidelines in [Section 5.1.2 Reduction in Dose of the Study Drug(s)].

ECGs are to be performed prior to obtaining the time-matched pharmacokinetic sample, therefore, the ECGs must be started at least 10 to 15 minutes before the pharmacokinetic draw. Whenever a study procedure coincides with the scheduled time point for an ECG

triplicate, the study activities will ideally be undertaken in a fixed sequence: ECG triplicate first, vital signs (blood pressure and heart rate) second and any type of blood draw as the last assessment. This order of events is not mandatory and can be changed if required in order to accommodate pharmacokinetic time points.

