5.1.2 Reduction in Dose of the Study Drug(s)

5.1.2.1 Gilteritinib Dose Reduction

Gilteritinib dose cannot be reduced during the DLT observation period (cycle 1/day 1 through cycle 1/day 28) of the phase 1 portion of the study.

Guidelines for gilteritinib dose interruption and reduction for the phase 2 portion are provided in [Table 5].

The dose levels potentially used include the following [Table 4]:

Table 4 Gilteritinib Dose Levels

Dose Level (DL)	Gilteritinib Dose
DL - 0	120 mg ^a
DL - 1	80 mg
DL - 2	40 mg

^a Starting dose for gilteritinib

The gilteritinib dose may be initially reduced by 1 dose level per day. The gilteritinib dose can be further reduced by a second dose level if the subject has already experienced clinical benefit. Note that dose reductions should occur in a step-wise manner. Only 2 dose level reductions are permitted. Dose reduction can occur during the treatment cycle based on the dose reduction guideline in [Table 5]. Additionally, if the investigator deems it necessary to ensure subject safety, dosing may be interrupted or reduced for reasons other than those provided in [Table 5]. In the unusual circumstance that dosing is interrupted or reduced for reasons not specified in the tables, the investigator should promptly inform the study medical monitor or his/her designee. If the gilteritinib dose has been reduced for related toxicities, it cannot be re-escalated. Any subjects that have been off treatment for more than 14 days other

than for HSCT or a study drug related AE, may only resume treatment after discussion with the medical monitor.

Table 5 Guidelines for Gilteritinib Dose Interruption or Reduction Event

Gilteritinib Dosing Instructions	
Nonhematological Events	
Grade 3 toxicity at least possibly related to gilteritinib	Dosing will be interrupted for up to 14 days. If the AE resolves to \leq grade 1 within 14 days, the subject may resume dosing at the reduced dose.
Grade 4 toxicity at least possibly related to gilteritinib	Treatment will be discontinued.
QTcF > 500 ms	See [Section 5.4.4]
Myelosuppression	

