3.2.2 Reduction in Dose of the Study Drug(s)

3.2.2.1 Gilteritinib Dose Reduction

Gilteritinib dose cannot be reduced during the DLT observation period (cycle 1/ day 1 through cycle 1 /day 28) of the phase 1 portion of the study.

Guidelines for gilteritinib dose interruption and reduction for the phase 2 portion are provided in [Table 3].

The dose levels potentially used include the following [Table 2]:

Table 2 Gilteritinib Dose Levels

Dose Level (DL)	Gilteritinib Dose
DL - 0	120 mg ^a
DL - 1	80 mg
DL - 2	40 mg

^a Starting dose for gilteritinib

The gilteritinib dose may be initially reduced by 1 dose level per day. The gilteritinib dose can be further reduced by a second dose level if the subject has already experienced clinical benefit. Note that dose reductions should occur in a step-wise manner. Only 2 dose level reductions are permitted. Dose reduction can occur during the treatment cycle based on the dose reduction guideline in [Table 3]. Additionally, if the investigator deems it necessary to ensure subject safety, dosing may be interrupted or reduced for reasons other than those provided in [Table 3]. In the unusual circumstance that dosing is interrupted or reduced for reasons not specified in the tables, the investigator should promptly inform the study medical monitor or his/her designee. If the gilteritinib dose has been reduced for related toxicities, it cannot be re-escalated. Any subjects that have been off treatment for more than 14 days other than for HSCT or a study drug related AE, may only resume treatment after discussion with the medical monitor.

Table 3 Guidelines for Gilteritinib Dose Interruption or Reduction Event

Gilteritinib Dosing Instructions	
Nonhematological Events	
Grade 3 toxicity at least possibly related to gilteritinib	Dosing will be interrupted for up to 14 days. If the AE resolves to \leq grade 1 within 14 days, the subject may resume dosing at the reduced dose.
Grade 4 toxicity at least possibly related to gilteritinib	Treatment will be discontinued.
QTcF > 500 ms	See [Protocol Section 5.4.4]
Myelosuppression	

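### The instruction for a confirmed QTcF above 500 ms orders a dose reduction that the phase 1 rules forbid in cycle 1, and it refers in a loop without QTcF-specific interruption or restart terms

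*Protocol*

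**What the plan says.** Protocol Section 5.4.4 sets the action: if a QTcF above 500 ms is confirmed, "then the investigator will interrupt and reduce gilteritinib per the interruption or reduction guidelines" found in Section 5.1.2. The step that leads to it applies whenever the threshold is crossed: "If the mean triplicate QTcF is > 500 ms at any time point, on local read", the ECG is repeated. Neither sentence is limited to a phase or a cycle. The same section sets the schedule: "A 12-lead ECG will be performed during the screening period, predose of cycle 1/day 1, cycle 1/day 8, cycle 1/day 15", then days 1 and 15 of each later cycle and the end-of-treatment visit.

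Protocol Section 5.1.2.1 opens with a restriction: "Gilteritinib dose cannot be reduced during the DLT observation period", which it defines as cycle 1/day 1 through cycle 1/day 28 of phase 1. No exception for QTcF is stated. It continues: "Guidelines for gilteritinib dose interruption and reduction for the phase 2 portion are provided in [Table 5". In that table the entry for a QTcF above 500 ms is only a pointer, "See [Section 5.4.4".

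SAP Section 3.2.2.1 repeats the phase 1 restriction and the phase 2 scope of the table. Its Table 3 gives the same kind of entry for QTcF, "See [Protocol Section 5.4.4".

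**The concern.** There are two linked problems.

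- **Conflict.** In the phase 1 DLT window, one section tells the investigator to reduce the dose and another says it cannot be reduced. A site that meets the event there must depart from one written instruction.
- **Loop.** A reader of 5.4.4 is sent to 5.1.2, whose QTcF row sends the reader back. The pause length and the restart condition for this event appear at neither end.

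The case is foreseeable: Protocol Section 1.3.1 lists QT prolongation among the expected reactions to gilteritinib. First at stake is a safety instruction that sites can follow consistently. Second is the 3+3 decision. Cohorts have 3 or 6 evaluable subjects, and in the absence of a DLT evaluability depends on the number of gilteritinib doses received, so an undefined interruption can change who is counted.

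**Working it through.** The plan states no figure to reproduce. The check sets the passages side by side, compares the timing, and does one piece of arithmetic.

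**1. The two rules compared**

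| | Protocol 5.4.4 | Protocol 5.1.2.1 |
|---|---|---|
| Trigger or period | Confirmed QTcF above 500 ms, any time point | Cycle 1 days 1 to 28, phase 1 |
| Interruption | Ordered | Not barred |
| Reduction | Ordered | Barred, no exception stated |
| Detail | Refers to 5.1.2 | Table 5, presented for phase 2; QTcF row refers to 5.4.4 |

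The only cell pair in direct conflict is reduction, and only inside the phase 1 window.

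**2. Can both rules apply at a scheduled visit?** The DLT window is days 1 to 28. Scheduled ECGs after the first dose fall on days 8 and 15, both inside it. The next, on cycle 2/day 1, is day 28 + 1 = 29, outside it. So there are two scheduled opportunities per phase 1 subject, plus any unscheduled ECG.

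**3. What the loop leaves out.** Following the references gives 5.4.4, then 5.1.2 and Table 5, then 5.4.4 again. SAP Table 3 and the ECG footnote of the Schedule of Assessments also lead to 5.4.4. What can be found along the way:

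- the action itself, in 5.4.4: repeat the ECG, seek a cardiology consult as medically indicated, and interrupt and reduce if confirmed;
- general rules in 5.1.2.1: the Table 4 dose levels, step-wise reduction, at most two reductions, no re-escalation after a reduction for related toxicity, and a medical-monitor discussion after certain absences of more than 14 days.

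No interruption length or restart condition is tied to QTcF. The Grade 3 row of Table 5 has both, but no passage says that it governs QTcF, which has its own row.

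**4. Effect on DLT evaluability.** Protocol Section 2.2.1 requires at least 23 of 28 gilteritinib doses, and at least 1 of 2 atezolizumab doses, in a subject without a DLT. Let k be the number of gilteritinib doses missed in cycle 1, assuming all others are taken. Doses received = 28 - k.

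- k = 5: 28 - 5 = 23, threshold met.
- k = 6: 28 - 6 = 22, not evaluable and may be replaced.
- k = 14: 28 - 14 = 14, not evaluable.

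The last line uses the upper limit in the Grade 3 row purely to illustrate how much the unstated length matters; the documents do not apply that limit to QTcF. A pause starting on day 8 could cost up to 21 doses (days 8 to 28), and one starting on day 15 up to 14 (days 15 to 28), so either ECG could lead to either result.

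**5. Limit on step 4.** A subject with a DLT is evaluable however many doses were taken. Under the DLT definition (Protocol Synopsis; SAP Section 6.2.1), a related non-hematologic toxicity of Grade 3 or higher is a DLT, and QT prolongation is not among the exceptions. The dose count therefore matters only when the event is judged unrelated or is graded below 3. The documents do not state the grade of a QTcF above 500 ms.

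**The case against.** **Section 5.4.4 is subject to 5.1.2.** It orders a reduction under the guidelines of 5.1.2, and the first rule there bars reduction in the window. On that reading a phase 1 site interrupts without reducing, and nothing is broken. This is a fair reading, and interruption is indeed not barred. But it makes the unconditional order to reduce wrong for phase 1 cycle 1, and the text does not say so. Another site could as reasonably treat the specific QTcF instruction as the exception.

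**Other clauses give room.** Section 5.1.2.1 lets the investigator interrupt or reduce for safety, but for reasons outside Table 5. QTcF is inside Table 5, and the clause is not said to override the phase 1 restriction. The immediate-hazard provisions (Protocol Sections 5.5.11 and 8.3) exist for departures from the plan; a named threshold with a planned response should not depend on them.

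**The loop is not empty.** This stands. A reader might infer that sites have no instruction at all, and the documents do not support that: 5.4.4 names the action and 5.1.2.1 gives general reduction steps. The gap is the QTcF-specific pause and restart terms.

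**The evaluability harm is conditional.** This stands too. A reader might infer that any such event in phase 1 removes the subject from the dose-finding count, but an event that is itself a DLT does not.

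**Which ECG reading governs.** Because 5.4.4 mentions a local read, a reader might infer that the governing reading is unclear. It is not. Section 5.4.4, the Schedule of Assessments footnote and SAP Section 7.5.4 all assign treatment decisions to the central reading; the local read concerns only the repeat ECG.

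**Few subjects are exposed.** The window is 28 days in up to 12 subjects, screened for QTcF, long QT syndrome and low potassium or magnesium. This limits the size but does not remove the conflict.

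**Conclusion.** The point holds and should be corrected. As written, Protocol Sections 5.4.4 and 5.1.2.1 cannot both be followed on dose reduction when a QTcF above 500 ms is confirmed in phase 1 cycle 1. Separately, the mutual reference between 5.4.4 and Table 5, repeated through SAP Table 3, leaves the QTcF-specific interruption length and restart condition unstated for any subject who has the event.

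The size is modest. The conflict covers reduction only, for 28 days in up to 12 subjects. The effect on the 3+3 count needs more than 5 missed gilteritinib doses and an event that is not a DLT. No expected frequency of QTcF above 500 ms is given, so the number of affected subjects cannot be estimated. The phase 2 two-stage test and its error rates are not involved. The conclusion rests on the current wording and takes no position on which instruction is clinically right.

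**What to change.** Reconcile Protocol Section 5.4.4, Section 5.1.2.1 with Table 5, and SAP Section 3.2.2.1 with Table 3:

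1. State the QTcF instruction in full in one place, including whatever interruption and restart terms the sponsor intends, and have the other places point to it in one direction only.
2. Say explicitly how the instruction applies in the phase 1 DLT observation period, and word the restriction in 5.1.2.1 to match.
3. Say whether Table 5 applies to phase 1 subjects at any time, since it is presented as phase 2 guidance.
4. Carry the same wording into the SAP.

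The content of the rule is for the sponsor's clinical team; none is proposed here. The cost is a wording amendment to the protocol and a matching SAP cross-reference. Sample size, endpoints and analysis methods stay as they are.
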